 5. Currently taking an allowed antidepressant treatment for at least 4 weeks prior to screening. The dose of the antidepressant medications should be as specified in Table 2 and Table 3. All primary and secondary antidepressant treatments must remain at a stable dose and frequency, without clinically significant adjustment. Randomization cannot take place until a minimum adequate duration of stable treatment, as specified in Table 2 and Table 3, has been achieved.
 6. HAM-D-17 score ≥24, CGI-S ≥5, and QIDS-SR-16 ≥19 at screening, and Visit 2/randomization
 7. Lifetime history of inadequate response, as described in Section 3.1, to at least 3 trials of antidepressant treatment of adequate dose and duration as specified in Table 1, Table 2, and Table 3. One of these trials must be the current treatment trial.
 8. Be able to understand and comply with the requirements of the study, as judged by the investigator
 9. Outpatient status at screening and enrollment (randomization) visits
 10. Capable of returning for study-related assessments, as judged by the investigator

For inclusion in the optional exploratory genetic sample collection, patients must fulfill the following criterion:

1. Provision of informed consent for genetic research

If a patient declines to participate in the optional genetic component of the study, there will be no penalty or loss of benefit to the patient. The patient will not be excluded from other aspects of the study described in this CSP, so long as they consent.

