except for patients testing positive for prescribed medications **that are otherwise permitted and there is no evidence of misuse, abuse, or dependence**. Patients can be re-tested only if either the initial THC, opiate, or barbiturate result is positive and they have a prescription, but the patient should be excluded if the result is still positive for THC, opiate, or barbiturate, respectively, at the second test. Patients with positive UDS for a drug(s) legally available by prescription must provide evidence of prescription for the drug(s).

10. Patients with a DSM-IV-TR Axis II disorder, which in the opinion of the investigator, has a major impact on the patient's current psychiatric status
11. Systolic BP <85 or >160 mmHg or diastolic BP >95 mmHg or heart rate <50 or >105 beats per minute at screening or randomization. Exclusionary values may be repeated once.
12. QTcF (Fridericia-corrected) \geq 450 msec at screening (Visit 1) or randomization
13. Patients who have had a suicide attempt within the last 6 months. Patients who, in the investigator's judgment, pose a significant suicide risk. Evidence of significant suicide risk may include any history of suicidal behavior and/or any suicidal ideation of type 4 or 5 on the C-SSRS in the last 6 months at screening or randomization.
14. Patients who are pregnant or lactating
15. Patients with unstable or inadequately controlled medical conditions (eg, unstable angina) or evidence of clinically relevant disease, eg, renal or hepatic impairment, symptomatic or significant coronary artery disease, cerebrovascular disease, viral hepatitis B or C, syphilis, or acquired immunodeficiency syndrome (AIDS). Hypothyroidism is permitted if corrected and the patient is on a stable treatment regimen for a minimum of 6 months. Combination of abnormal thyroid-stimulating hormone (TSH) test results and abnormal free thyroxine levels require discussion with Sponsor or Sponsor's representative.
16. Patients with diabetes mellitus fulfilling any of the following criteria:
 - Unstable diabetes mellitus defined as glycosylated hemoglobin (HbA_{1c}) >8.5% at screening
 - Admitted to hospital for treatment of diabetes mellitus or diabetes mellitus-related illness in the past 12 weeks
 - Not under physician care for diabetes mellitus

- Has not been on the same dose of oral hypoglycaemic drug(s) and/or diet for the 4 weeks prior to screening. For thiazolidinediones (glitazones) this period should not be less than 8 weeks.

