6.2.1.1 Screening visit (Visit 1)

This section describes the preferred order of assessments; however, this order is not mandatory, except that QIDS-SR-16 and S-STS must be done first. Note, that the assessments to be performed during the screening visit can be completed over 2 days if agreed upon with medical advisor.

During the screening visit, the QIDS-SR-16 and S-STS (self report) will be administered first.

Prior to conducting any further procedures, the QIDS-SR-16 should be independently scored (without review by the investigator) and if the inclusion criterion score of ≥ 19 is not met, no further study procedures are to be conducted and the patient will not be randomized. At no time may the patient be informed of the inclusion criterion score on the QIDS-SR-16. If the QIDS-SR-16 criterion is met, the HAM-D-17 interview will be conducted and the CGI-S will be completed to determine whether the patient meets the inclusion criteria of a HAM-D-17 total score ≥ 24 and CGI-S ≥ 5 . If these criteria are not met, no further procedures are to be conducted and the patient will not be randomized. If these criteria are met, the MINI interview will be conducted.

While completing Module B of the MINI (suicidality), the investigator will review the S-STS self report responses and inquire further into any suicidal ideation that was reported. During this portion of the interview, the investigator will also complete the C-SSRS baseline version. If the patient is judged by the investigator to pose a significant suicide risk, the patient will not be enrolled and the investigator will take appropriate steps to assure the patient's safety. Evidence of significant suicide risk may include any history of suicidal attempt or behavior and/or any suicidal ideation of type 4 or 5 on the C-SSRS in the last 6 months.

██████████

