6.4.9.6 Columbia-Suicide Severity Rating Scale (C-SSRS)

The C-SSRS is a unique, simple and short method of assessing both behavior and ideation that tracks all suicidal events, and provides a summary of suicidality (Posner et al 2007). It assesses the lethality of attempts and other features of ideation (frequency, duration, controllability, reasons for ideation and deterrents), all of which are significantly predictive of completed suicide.

The C-SSRS will be administered at the screening visit and at each scheduled visit throughout the study by a trained rater. The trained rater will record the clinical observation on the scale, which will be used as the source document. If at all possible, the same individual should perform the assessment at each visit to reduce scoring variability. In the event the primary rater is not available, a designated back-up rater who meets the same qualifications may perform the C-SSRS.

The C-SSRS must be administered at designated visits after the infusion.

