11.2 Calculation or derivation of safety variables

A treatment-emergent AE (TEAE) is defined as any AE that started on or after the first dose of IP up to 30 days after the last dose of IP. An AE already present at the time of the first dose of IP that worsens in intensity following exposure to IP or an AE with an unknown/not reported onset date will also be considered as treatment emergent.

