11.2.6 Other safety assessments

11.2.6.1 C-SSRS

Occurrence of suicidal behavior after baseline up to Week 3 will be defined as having answered “yes” to at least 1 of the 4 suicidal behavior subcategories (actual attempt, interrupted attempt, aborted attempt, and preparatory acts or behavior) at any post-baseline evaluation.

Occurrence of suicidal ideation after baseline up to Week 3 will be defined as having answered “yes” to at least 1 of the 5 suicidal ideation subcategories (wish to be dead, non-specific active suicidal thoughts, active suicidal ideation with any methods [no plan] without intent to act, active suicidal ideation with some intent to act [without specific plan], and active suicidal ideation with specific plan and intent) at any post-baseline evaluation.

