12.2.4 Safety analyses

Adverse events will be coded using the MedDRA. For each study treatment, numbers of events and crude incidence rates will be tabulated by preferred term and system organ class. An event that occurred 1 or more times on the date of, or subsequent to, randomization will contribute 1 observation to the numerator of the crude incidence rate. The denominator of the rate will comprise all randomized patients exposed to the study treatment. If the intensity or seriousness of the AE changes, the overall intensity or seriousness will be the maximum intensity or seriousness of the multiple occurrences.

Serious adverse events, AEs leading to death, and AEs leading to withdrawal of patients will be tabulated for each treatment group. Commonly occurring AEs, ie, those which occur in 5% or more of the patients in either treatment group, will be summarized using descriptive statistics.

Descriptive statistics will be used to present the safety outcomes including incidences and severity of AEs and SAEs; incidences of AEs leading to treatment discontinuation and study withdrawal, incidences of AEs associated with suicidality, and incidences of OAEs; changes from baseline in physical examination results, weight, BMI, vital signs, clinical laboratory test

results, and ECG results; suicidality as assessed by C-SSRS; and changes from baseline in CADSS total scores.

All laboratory test results, vital signs, ECG results, weight, and BMI will be summarized for each treatment group using descriptive statistics at each visit for raw numbers and change from baseline. The proportions of patients who have a weight gain $\geq 7\%$ compared with baseline will be tabulated.

Suicidality measures based on the STS and the C-SSRS will be summarized for each treatment group using descriptive statistics at each assessment.

The results of the PK and pharmacogenetic analyses will be presented in reports separate from the CSR.

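### The C-SSRS ideation variable ignores the baseline rating, so it mixes pre-existing with new or worsening ideation and dilutes any difference between arms

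*Protocol*

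**What the plan says.** Protocol Section 11.2.6.1 fixes the derivation. A single positive answer is enough: the patient must respond positively "to at least 1 of the 5 suicidal ideation subcategories (wish to be dead" is the first entry and a specific plan with intent the last), and this may happen at any evaluation after baseline. The sentence also sets a limit at Week 3. No condition is placed on what the patient answered at baseline, and the five categories carry equal weight.

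A reference value exists. At screening, Section 6.2.1.1 says that "the investigator will also complete the C-SSRS baseline version". After that, Section 6.4.9.6 states: "The C-SSRS will be administered at the screening visit and at each scheduled visit throughout the study by a trained rater".

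On entry, exclusion criterion 13 (Section 4.2) removes patients with a suicide attempt in the last 6 months and those the investigator judges a significant risk. The evidence for that judgment may include "any suicidal ideation of type 4 or 5 on the C-SSRS in the last 6 months at screening or randomization". Types 1 to 3 are not named. Entry also requires severe depression: "HAM-D-17 score ≥24, CGI-S ≥5, and QIDS-SR-16 ≥19 at screening, and Visit 2/randomization" (Section 4.1).

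The planned analysis is descriptive. Section 12.2.4 says: "Suicidality measures based on the STS and the C-SSRS will be summarized for each treatment group using descriptive statistics at each assessment".

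**The concern.** Suicidality by C-SSRS is a named safety objective (Section 2.3). For a safety question, the informative event is ideation that appears or gets worse after the first dose. The variable in Section 11.2.6.1 does not isolate that event. A patient with an unchanged wish to be dead is an occurrence; a patient who goes from that to a plan with intent is the same occurrence.

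Elsewhere in the same chapter the protocol does use baseline. An adverse event already present at the first dose is treatment-emergent only if it is one "that worsens in intensity following exposure to IP" (Section 11.2). Laboratory values, ECG, vital signs and CADSS are all changes from baseline. This is an analogy rather than a contradiction, but it shows that the ideation variable is the odd one out. If it is reported as defined, a real increase in emergent ideation could appear as a small difference on top of a common background rate.

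**Working it through.** **No figure to reproduce.** The protocol gives no rate, margin or power for this variable. The only trial figure used below is the arm size of 94 (Section 12.3: 84 / 0.90 = 93.3, rounded up to 94; 3 × 94 = 282).

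**What the definition does to single patients** (screening category, then worst category after the first dose):

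- 1 then 1: occurrence, although nothing changed.
- 1 then 5: occurrence, indistinguishable from the patient above.
- 0 then 1: occurrence, the only one of the three that is new onset.

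**Dilution between arms.** Assumptions, none of them in the protocol:

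- b = share of patients with type 1 to 3 ideation at baseline, 10% to 70%.
- q = chance that such a patient answers yes again in the window, 90% (range 80% to 100%).
- p = true emergent ideation, 5% on placebo and 15% on drug, a ratio of 3.0.

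The rate that the variable reports is b × q + (1 − b) × p. At b = 10%, placebo is 0.10 × 0.90 + 0.90 × 0.05 = 13.5% and drug is 0.10 × 0.90 + 0.90 × 0.15 = 22.5%.

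| b | placebo | drug | difference | ratio |
|---|---|---|---|---|
| 10% | 13.5% | 22.5% | 9 points | 1.67 |
| 30% | 30.5% | 37.5% | 7 points | 1.23 |
| 50% | 47.5% | 52.5% | 5 points | 1.11 |
| 70% | 64.5% | 67.5% | 3 points | 1.05 |

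The difference is (1 − b) × 10 points whatever q is. Changing q to 80% or 100% moves the ratio only to 1.72 or 1.62 at b = 10%, and to 1.12 or 1.10 at b = 50%.

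**Power, for scale only.** The protocol plans no test on C-SSRS. With 94 per arm and a two-sided 5% level, a normal approximation gives 0.36, 0.17, 0.10 and 0.06 for the four rows. A new-or-worse variable in all patients at 5% against 15% has 0.63 (0.55 with Fisher's exact test). If only new onset in patients without baseline ideation is counted, power is 0.58, 0.48, 0.36 and 0.24. The baseline-aware versions do better in every row, but none is well powered.

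**Number of ratings in the window.** The definition stops at Week 3. Table 4 gives Visits 3 to 10 (8 ratings) plus the post-infusion rating at Visit 2, so 9. The full schedule after the first dose is Visits 2 to 16 plus Week 14, so 16. Seven ratings (Visits 11 to 16 and Week 14) fall outside the variable, although the same sentence speaks of any evaluation after baseline and treatment lasts 12 weeks. The behavior variable in the same section carries the same limit.

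**Which rating is pre-dose.** Sections 6.2.1.2 and 6.3.1 place the Visit 2 C-SSRS after the infusion. The screening rating, up to 42 days before Day 1, is therefore the only scheduled one before the first dose.

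**The case against.** The strongest case on the other side has four parts.

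- **Other measures exist.** The protocol also has a C-SSRS behavior variable, adverse events of suicidality with separate eCRF pages (Section 6.4.3), C-SSRS and S-STS summaries at each assessment (Section 12.2.4), and S-STS change from baseline, which is baseline-adjusted. This stands in part. The S-STS analysis is exploratory, self-reported and taken before infusion, and in Weeks 2 and 3 only at Visits 5 and 8. Symptoms found during ratings are generally adverse events only if serious or a cause of discontinuation (Section 6.3.2). Strong suicidal thoughts are reportable, but a rise from type 1 to type 3 may not be. No within-patient worsening on the C-SSRS is defined.
- **The size is assumed.** This stands. The protocol gives no baseline prevalence, and criterion 13 may keep it low; at 10% much of the difference is still visible.
- **Shift tables may be in the SAP.** They may, and their absence here is not the point. The point is the derivation that the protocol does state.
- **A baseline-aware variable needs a sound baseline.** This stands and shapes the fix. Criterion 13 looks back 6 months. If that recall sets the baseline category, a six-month worst value is compared with short intervals between visits, and real worsening can be missed.

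A reader might infer more: that ideation present at entry swamps everything new, so that the trial can hardly show a suicidality harm at all. The documents do not support that. Without a prevalence, swamping cannot be shown; randomization keeps the comparison between arms unbiased; and this is one derived variable among several.

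**Conclusion.** The point holds for this one variable. As defined in Section 11.2.6.1, it cannot separate pre-existing from new or worsening ideation and cannot show a rise in category within a patient. The consequence is dilution, which grows with baseline prevalence: under the stated assumptions a ratio of 3.0 is reported as about 1.7 at 10% prevalence, about 1.1 at 50% and 1.05 at 70%. Those figures rest on assumed rates and show direction and order of size only. Because the safety analysis is descriptive, the compressed rates and ratio are what a reader of the report would see; the power figures are secondary. The Week 3 limit is a separate and plainer inconsistency in the same definition, and should be settled at the same time.

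**What to change.** In Section 11.2.6.1:

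- Add treatment-emergent ideation: the worst category (0 to 5) after the first dose is higher than the pre-dose baseline category.
- Add emergent type 4 or 5 ideation in patients without it at baseline.
- Name the screening C-SSRS as the baseline, because the Visit 2 rating follows the infusion, and state which recall period sets the baseline category.
- Tabulate both variables by arm, with a shift table of baseline category by worst later category. Keep the any-yes rate as a descriptive line.
- Reconcile the Week 3 limit with the reference to any evaluation after baseline and with the C-SSRS schedule to Week 14, for both the ideation and the behavior variables.

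The cost is one more derivation and one more table, using ratings that the protocol already schedules. The drawback is a baseline that may be up to 42 days old, which should be stated beside the table.

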11.2.6.2 CADSS

The CADSS is a 23 item self-report scale ([Bremner et al 1998](#)). It is a reliable, valid self-report instrument. The severity of each dissociative symptom range from 0 (not present) to 4 (extreme). The change from baseline at each scheduled assessment in CADSS total score will be calculated.

11.2.6.3 CogState

Outcome measures of CogState Battery

For each cognitive task, a single primary outcome measure was selected from each test in the battery to minimize experiment-wise error rates. Each primary outcome measure was selected because it has been shown to be optimal for the detection of change because:

- it is drawn from a data distribution that contains only a small probability of floor or ceiling effects and no restriction in the range of possible performance values.

- it is drawn from a distribution that is distributed normally or which can be corrected to normal through the use of appropriate mathematical transformation (e.g., logarithmic base 10, or arcsine).

Table 11 summarizes the primary outcome measures for each task in CogState battery the operational definition and the variable code.

Table 11 CogState outcome measures and the cognitive tasks

Task name	Major cognitive domain	Unit of measurement	Description
Detection Task*	Psychomotor speed	Log10 milliseconds	Speed of performance; mean of the log10 transformed reaction times for correct responses (lower score = better performance)
Identification Task*	Attention/vigilance	Log10 milliseconds	Speed of performance; mean of the log10 transformed reaction times for correct responses (lower score = better performance)
One-card Learning*	Visual learning	Arcsine proportion correct	Accuracy of performance; arcsine transformation of the proportion of correct responses (higher score = better performance)
One-back	Working memory	Arcsine proportion correct	Accuracy of performance; arcsine transformation of the proportion of correct responses (higher score = better performance)

11.3 Calculation or derivation of patient reported outcome variables

11.3.1 SDS

The SDS total score will be calculated as the sum of the scores for the 3 inter-correlated domains (school/work, social life, and family life/home responsibilities). Each domain score can range from 0 to 10 and the total score can range from 0 to 30. The total score will be calculated only for patients who rate all 3 domains. Change from randomization will be calculated for the total score and for each domain score.

11.4 Calculation or derivation of pharmacokinetics variables

The population PK analysis will be performed by AstraZeneca Research and Development. AZD6765 plasma concentration-time data from this study and other prior and/or future studies may be pooled and subjected to analysis using non-linear mixed effects modeling, in order to build a population model to describe the PK of AZD6765 in patients with MDD. Together with safety data and efficacy/PD data, this may be subjected to exploratory population PK/PD analyses. A population PK analysis plan will be produced prior to any such investigations, and the analysis will be reported separately.

11.4.1 Pharmacokinetics analysis method

Population PK will be performed on the plasma concentrations of AZD6765 using the “population PK approach.”

11.5 Calculation or derivation of pharmacodynamic variables

See Section 11.1 for details.

The biomarker panel will be analyzed by Rules Based Medicine. The data will be analyzed separately and the results may be included in the CSR.

11.6 Calculation or derivation of pharmacogenetic variables

Results from the optional exploratory genetic research performed will be reported separately from the CSR.

12. STATISTICAL METHODS AND SAMPLE SIZE DETERMINATION BY ASTRAZENECA OR DELEGATE

12.1 Description of analysis sets

12.1.1 Efficacy analysis sets

12.1.1.1 Modified intent-to-treat (mITT) analysis set

The mITT analysis set will include all randomized patients, who took IP and who have a baseline MADRS total score assessment and at least 1 post-baseline MADRS total score classified according to their randomized treatment. The mITT analysis set will be used for the efficacy analyses.

12.1.1.2 Per-protocol (PP) analysis set

The PP analysis set will include only those mITT patients who have no significant protocol deviation, and who received the treatment to which they were randomized. The Statistical Analysis Plan (SAP) will provide the exact criteria for defining the PP analysis set. The analysis of the primary efficacy variable will be repeated on the PP analysis set, and additional analyses of efficacy variables may be performed using the PP analysis set to assess the robustness of the treatment effects.

12.1.2 Safety analysis set

The safety analysis set will include all randomized patients who were given at least 1 dose of IP, and for whom any post-dose data are available and are classified according to the treatment actually received. That is, erroneously treated patients (eg, those randomized to Treatment A, but actually given Treatment B) will be accounted for in their actual treatment group. The safety analysis set will be used to assess safety and tolerability variables.

12.2 Methods of statistical analyses

Details of the statistical analysis methods will be provided in a comprehensive SAP that will be prepared and finalized prior to unblinding.

In general, all efficacy, safety, and PK variables will be summarized using descriptive statistics and graphs as appropriate. Continuous variables will be summarized by descriptive statistics (sample size (n), mean standard deviation (SD), median, minimum and maximum). For PK variables, the geometric mean and CV will be used instead of the arithmetic mean and SD, if appropriate. Categorical variables will be summarized in frequency tables (n, frequencies, and percentages). Individual patient data will be presented in listings.

All statistical tests will be conducted at a 2-sided significance level of 5% unless otherwise specified. In general, each of the AZD6765iv dose groups (50 mg and 100 mg) will be compared with the placebo group. Where appropriate, model-based point estimates, together with their 95% CIs, will be presented along with the 2-sided p-value for the test.

